3.3. PHASE 2A EXPANSION GROUPS

The Phase 2a Dose Expansion groups include approximately 94 patients:

Phase 2: Expansion Groups

- Group 1: Extremity STS
 - Anthracycline naïve patients with soft tissue sarcomas of the extremity AJCC Stage III OR select IV (>5 cm injectable tumors) locally advanced and or metastatic disease not amendable to definitive surgical intervention at presentation, according to a multidisciplinary treatment team determined prior to screening. The following anthracycline sensitive histologies are allowed: angiosarcomas, leiomyosarcoma, liposarcoma, synovial sarcoma, adult fibrosarcoma, and undifferentiated pleomorphic sarcoma.
- Group 2: Unresectable STS
 - Anthracycline naïve patients with locally advanced or metastatic, unresectable, STS with defined anthracycline sensitive (expected historical ORR ~20%) histologies angiosarcomas, leiomyosarcoma, liposarcoma, synovial sarcoma, adult fibrosarcoma, and undifferentiated pleomorphic sarcoma.
- Group 3a: Head and Neck
 - Anthracycline naïve patients with histologically or cytologically confirmed relapsed or metastatic squamous-cell carcinoma of the head and neck, not suitable for further radical local treatment or patients with distant metastases who are treatment naïve or may have received two or less systemic therapies (chemotherapy and/or immunotherapy).

Figure 4: Phase 2a Dose Expansion Groups

3.4. STUDY-WIDE TREATMENT INTERRUPTION RULES

The study may be interrupted or stopped at any time based upon the Sponsor's and/or the SRC's review of the safety data. The study may resume once assessment by the SRC is complete, and an acceptable corrective action plan is implemented by the sponsor.

If the study is temporarily interrupted or permanently terminated, the Sponsor will inform study sites, the Institutional Review Board (IRB) / Independent Ethics Committee (IEC), and the appropriate regulatory bodies.

3.5. RATIONALE FOR STUDY DESIGN AND DOSE

3.5.1. Rationale for Study Design and Objectives

This is a first-in-human, Phase 1/2a study in patients with advanced solid tumors. Phase 1 will explore escalating doses of SQP33 protodrug and SQL70 biopolymer (see section [3.1 Overview](#)) to identify the MTD and/or RP2D of SQP33 protodrug with 10 mL and/or 20 mL of SQL70 biopolymer. The accelerated titration and 3+3 (Rolling 6) design are being used to evaluate safety and tolerability of SQ3370. During the study, PK will be evaluated to determine the amount of systemic and localized active Dox following SQ3370 treatment.

Phase 2a will utilize the RP2D determined in Phase 1. Three Expansion Groups will further explore the safety and preliminary efficacy of SQ3370 in different patient populations.

Group 1: Advanced High-risk Soft Tissue Sarcoma of the Extremity

Resectable is defined for the study as a primary surgical intervention that is thought to produce a surgical cure and maintain a good functional outcome of the affected extremity. The study will enroll patients with unresectable soft tissue sarcomas of the extremity AJCC III OR select IV (>5 cm injectable tumors) locally advanced and or metastatic that meet the preceding injectable tumor criteria not amendable to primary surgical intervention according to the consensus of multidisciplinary treatment team, determined prior to screening.

The study will be conducted in 2 phases with a Simon 2 stage design in the 2nd phase. The group will open with the initial phase safety run-in of patients to establish the safety and initial feasibility of a 12-week delay in definitive surgical resection in patients with high-risk STS of the extremity treated with SQ3370, after review by the safety steering committee the Simon 2 stage design will initiate subjects enrolled in the lead-in will contribute to this phase of the study.

Patients will enroll at the RP2D of SQ3370 as anticipated that the size of tumors given the stage (≥ 2) will receive a fixed dose of SQL70 (20 mL). All patients are planned to receive 2 cycles of SQ3370 and undergo a disease reevaluation per RECIST 1.1. All patients without evidence of disease progression after 2 cycles, will then undergo an additional 2 cycles of treatment and have a presurgical disease re-evaluation and proceed to definitive surgical procedure(s) of the extremity tumor.

Only patients who have had objective evidence of response or whom in the opinion of the multidisciplinary treatment team determined to have achieved a clinical benefit may defer surgery at this point, the study will allow up to 4 additional cycles pre-operatively, at which point all patients should undergo exploratory surgery and or extremity tumor resection.

If a patient had a response, they may receive up to 4 additional cycles post operatively but not to exceed 12 cycles within the study. Surgical markers will be used to indicate the tumor bed for injection with SQL3370 or if suitable for the metastatic patients, a metastatic lesion may be injected.

Any patient at any point who has been determined to have progressive disease has reached the end of treatment and will proceed to a definitive surgical treatment, note pre-operative radiation is allowed on study for patients with progressive disease preoperatively. It is encouraged to keep subjects on study and to evaluate surgical specimens as per planned biomarker and pathological assessments.

Patients who undergo surgical resection and have had good response as defined by necrosis on histopathological resection may continue for additional treatment post-operatively. If post op radiation is administered the subjects come off treatment (see [3.1.5 End of Treatment](#) for details) and will remain on study in Long Term Follow-up.

Safety Monitoring

The Study will use a safety-run-in to evaluate the PK and tolerability when at least 6 subjects have been enrolled and completed at least the planned Cycle 1. All available safety tolerability data will be presented and discussed at the SRC.

If after the evaluation by the SRC the study proceeds after evaluation of the initial subjects a second evaluation as defined in the statistical section. An evaluation of the totality of the data available to complete the planned 4 cycles and to review efficacy and histopathological response data and will provide the sponsor a recommendation as to proceed with expansion or to halt enrollment of the group.

Group 2: Comparison of the RP2D of SQP33 Administered Over 3 vs 5 Days

Compare safety and tolerability of the RP2D in two infusion schedules of SQP33 (3-day vs 5-day) in locally advanced, unresectable, STS who are anthracycline naïve and with defined anthracycline sensitive (expected historical ORR ~20%) histologies angiosarcomas, leiomyosarcoma, liposarcoma, synovial sarcoma, adult fibrosarcoma, and undifferentiated pleomorphic sarcoma.

Each treatment group will maintain the total dose of SQP33 per cycle constant and compare 2 different infusion schedules, a 3-day vs a 5-day schedule. The study will be guided by the Continuous Reassessment Method (CRM) design. The CRM model provides an indication of whether to alter the RP2D regimen (3-day dosing per 21-day cycle vs. 5-day dosing per 21-day cycle) based on a comparison of toxicity and efficacy data collected from participants enrolled. The participants will receive SQP33 at the RP2D administered IV as a 3-day dosing regimen per 21-day cycle or as a 5-day dosing regimen per 21-day cycle.

A toxicity rate at or above 15% for myelosuppression (Grade ≥ 3) related treatment emergent adverse events (TEAEs) (anemia and febrile neutropenia) would be considered unsafe for the cohort, and enrollment would stop. If the 3-day infusion is not well tolerated that group will close, the study will continue with the RP2D and 5-day schedule with the initial adaptive design phase.

Safety Monitoring

All available safety tolerability data will be presented and discussed at the SRC. The maximum inefficacy and minimum efficacy rates are based on historical ORR, with <20% ORR being undesirable, and >35% ORR being desirable. Up to 11 participants per arm will be enrolled. After approximately half (n=6 per arm) of participants in Expansion Group 2 have been enrolled and observed for at least 2 cycles or approximately 6-weeks and have had at least one post-baseline tumor assessment, an evaluation of all available data (safety, efficacy, and PK from both the Expansion and Dose Escalation parts of the study) will be performed by the SRC.

Group 3a: Head and Neck

The study will enroll patients with relapsed or metastatic head and neck tumors with advanced disease and historically poor outcomes and limited objective responses to currently available therapies. Patients will be selected with histologically or cytologically confirmed squamous-cell carcinoma of the head and neck who meet any of the following 1) confirmed relapsed squamous-cell carcinoma of the head and neck, 2) metastatic at initial presentation squamous-cell carcinoma of the head and neck, 3) patients with locally advanced head and neck cancer pretreated with surgery and/or radiotherapy and not suitable for further radical local treatment, 4) patients with distant metastases who may have received one or less chemotherapy regimen.

Patients will be treated with the RP2D of SQP33 with the SQL70 biopolymer dose fixed at 10 mL, every 21 days (1 cycle) up to 12 cycles or until the subject has PD, withdraws consent, Investigator decision, or death. On Day 1 of each cycle, the subject will receive an injection of the SQL70 biopolymer into the tumor, followed by five (5) days of SQP33 infusion at the RP2D. Sample sizes be guided by a Simon 2-stage (optimal) designs based on historical objective responses (see statistical section for details). Enrollment will be continued after reaching the indicated number of participants at Stage 1 while the initial efficacy evaluation is ongoing.

Safety Monitoring

All available safety tolerability data will be presented and discussed at the SRC after 13 evaluable subjects have been enrolled and a recommendation will be made to the sponsor to continue or terminate the group enrollment based on ORR and totality of the data.

3.5.2. Rationale for Dose and Dosing Interval

SQL70 biopolymer will be administered intra and/or peritumorally at a dose of either 10 mL or 20 mL injection volume. The 10 mL dose is intended for a single lesion or cluster of lesions, and the 20 mL dose in Phase 1 was explored for concurrent treatment of 2 lesions, or for a single larger lesion (see sections [3.1.4.4 Phase 1: 20 mL SQL70 Biopolymer \(post-Cycle 1\) Cohort](#) and [3.2.3 Phase 1: 20 mL SQL70 Biopolymer \(from Cycle 1\) Cohort](#)).

The dose volume of SQL70 biopolymer is expected to provide sufficient coverage for tumors of varying sizes and enable the local release of active Dox from escalating doses of SQP33 protodrug infusions, while taking into consideration practical limitations and historical precedent for local tumor injections.

High injection volumes of SQL70 biopolymer were performed in absolute terms (15 mL) in the GLP study SQ3370-TOX-108 in dogs and were well tolerated. The use of a single dose (10 mL) of SQL70 biopolymer was explored with escalating doses of SQP33 protodrug in SQ3370-TOX-108 and SQ3370-TOX-109. Based on allometric scaling by body surface area (BSA), this design introduces an extra margin of safety for human patients who have approximately 3.24-times the BSA of dogs but will still be injected locally with only 10 mL or 20 mL of SQL70 biopolymer.

The starting daily dose of SQP33 protodrug for this clinical study is 8 mg/m²/day (5.72 mg/m²/day Dox Eq).

The starting human dose of SQP33 protodrug with a fixed amount of SQL70 biopolymer was determined in accordance with ICH S9 guidelines, which propose using 1/6th of the human equivalent dose HNSTD taken from a GLP toxicology study in the relevant species.

The dose of SQP33 protodrug is rounded down from the suggested starting dose from the GLP toxicology study SQ3370-TOX-108 in dogs. SQP33 protodrug infusions are given daily on Day 1 through Day 5. The starting total dose per cycle of SQP33 protodrug will be 40 mg/m²/cycle (28.6 mg/m²/cycle Dox Eq).

This starting dose is anticipated to be well-tolerated, as the total dose per cycle is less than half of the 75 mg/m² recommended systemic clinical dose per cycle of Dox HCl. Additionally, the starting dose is less than half of the no-observed-adverse-effect level (NOAEL) found in the GLP toxicology study SQ3370-TOX-108.

No additional safety margins were included as conventional Dox and Dox-containing products are well-characterized agents with known risks. The nonclinical studies suggest that the clinical side effect profile of SQ3370 would be similar to that of conventional Dox, with myelosuppression as the expected major toxicity.

4. PATIENT POPULATION

All patients in all Phase 1 cohorts and Phase 2a expansion groups must meet the inclusion and exclusion criteria below.

4.1. GENERAL INCLUSION/EXCLUSION CRITERIA FOR PHASE 1 COHORTS AND PHASE 2A EXPANSION GROUPS

4.1.1. Inclusion Criteria

Patients are eligible to be included in the study only if all the criteria below apply.

1. Able to provide written informed consent and understand and comply with the requirements of the study.
2. Patients ≥ 18 years of age on the day of signing the Informed Consent Form (ICF).
3. Histologically or cytologically confirmed cancer or desmoid tumor. Confirmation is not required for each individual lesion, and it is not required for the tumor selected for injection.
 - *Additional Criteria for Phase 1 Dose Escalation Cohorts:* tumor is either refractory to or relapsed following standard of care or ineligible for standard of care therapy
4. There must be an injectable tumor defined as all the following:
 - a. measurable per RECIST v1.1 at baseline
 - b. palpable or able to be injected percutaneously
 - c. not involving the following organs/structures: pancreas and extrahepatic biliary tract, central nervous system, or heart and great vessels
 - d. accessible by repeated intratumoral or peritumoral injection with an 18- to 22-gauge needle
 - *Additional criteria the 20 mL SQL70 biopolymer cohorts in Phase 1 Cohort:*
 - Have at least two injectable lesions or, based on investigator discretion and Medical Monitor approval, a large single lesion (approximately 5 cm or larger).
5. Eastern Cooperative Oncology Group (ECOG) performance status score 0-1 (except for Group 3a, Head & Neck, where 0-2 is acceptable).
6. Adequate hematologic function¹ as defined by:
 - a. absolute neutrophil count ≥ 1500 mL
 - b. hemoglobin ≥ 9.0 g/dL
 - c. platelet count $\geq 100,000$ /mL
7. Adequate hepatic function as defined by:
 - a. total bilirubin ≤ 1.2 mg/dL (unless the elevation is due to Gilbert's Syndrome)

¹ This should reflect baseline hematological function and cannot be on growth factor supported agents, e.g. G-CSF, GM-CSF or erythropoietin stimulating.

- b. aspartate transaminase (AST) and alanine transaminase (ALT) $\leq 3.0 \times$ the upper limit of normal (ULN)
- 8. Adequate renal function as defined by creatinine clearance ≥ 45 mL/min according to the Cockcroft-Gault equation or a 24-hour urinary creatinine test.
- 9. Adequate coagulation function as defined by international normalized ratio ≤ 1.5 and a partial thromboplastin time ≤ 5 seconds above the ULN.
- 10. Resolution to Grade ≤ 1 AEs by the NCI-CTCAE v5.0 of all clinically significant toxic effects of prior locoregional treatment, surgery, chemoembolization, or other anticancer treatment. Exceptions to this are Grade ≥ 1 toxicities, which, in the opinion of the Investigator and the Sponsor, are stable, and should not exclude the patient (i.e., alopecia, neuropathy, and autoimmune complications of immunotherapy, such as well managed diabetes, hypothyroidism, or hyperthyroidism controlled on hormone replacement therapy).
- 11. Women of childbearing potential and sexually active males agree to use highly effective contraception for the duration of study participation and for 90 days after the last dose of study treatment

4.1.2. Exclusion Criteria

Patients are excluded from the study if any of the criteria below apply.

- 1. Prior lifetime exposure to >300 mg/m² of Dox HCl or DOXIL / CAELYX® or 600 mg/m² of epirubicin HCl or 600 mg/m² daunorubicin prior to study dosing.
- 2. CHF, severe myocardial insufficiency, or cardiac arrhythmia, including any one of the following:
 - a. Echocardiogram (ECHO) or multigated acquisition (MUGA) scan with an actual left ventricular ejection fraction (LVEF) $\leq 45\%$, within 28 days prior to Cycle 1 Day 1.
 - b. Clinically significant cardiac arrhythmias (e.g., ventricular tachycardia), complete left bundle branch block, high-grade atrioventricular (AV) block (e.g., bifascicular block, Mobitz type II, and third-degree AV block).
 - c. Conduction abnormalities that would prevent accurate diagnostic assessment of ventricular function, such as atrial fibrillation with rapid ventricular response.
 - d. Symptomatic CHF.
 - e. Screening QTc >470 msec and/or previous history of QT prolongation while taking other medications.
 - f. History or signs of active coronary artery disease with or without angina pectoris within the last 6 months.
- 3. Any of the following within 28 days* prior to Cycle 1 Day 1 (i.e., Day -28 is the day after the last dose / procedure):
 - a. Major surgery, as defined by the Investigator.
 - b. Radiotherapy.

- c. Chemotherapy, immunotherapy, and/or anticancer therapy. If the agent is a small molecule therapeutics, only 6 elimination half-lives are required before the patient is eligible.
- d. An investigational product. If the agent is a small molecule investigational product, only 6 elimination half-lives are required before the patient is eligible.
- e. Currently enrolled in a clinical study involving an investigational product, or concurrently enrolled in any other type of medical research judged not to be scientifically or medically compatible with this study.

*1-2 days less may be allowed with Medical Monitor approval so as not to delay the start of SQ3370 treatment which, due to the 5 days of dosing, typically needs to begin on a Monday

- 4. Trastuzumab or trastuzumab emtansine dosed within 7 months prior to Cycle 1 Day 1.
- 5. Any transfusion within 14 days prior to Cycle 1 Day 1.
- 6. Pregnant or breast-feeding women.
- 7. Patients that are either positive for hepatitis B surface antigen (HBsAg) and/or detectable hepatitis B virus (HBV) DNA. HBcAb positivity will be allowed if one or both of the following is true: a) hepatitis B surface antibody is present or b) hepatitis B DNA testing is negative and the patient is receiving hepatitis B reactivation prophylaxis with entecavir, tenofovir, telbivudine or lamivudine.
- 8. Patients with hepatitis C; unless they have completed a course of antiviral therapy and have undetectable levels of HCV ribonucleic acid.
- 9. Has a known diagnosis of immunodeficiency or is receiving either chronic systemic steroid therapy or any other form of immunosuppressive therapy within 7 days prior to Day 1 Cycle 1, except in the case of central nervous system (CNS) metastases. The use of physiologic doses of prednisone 10 mg/day or its equivalent is permitted.
- 10. Patients with symptomatic concurrent conditions such as pleural effusion, ascites, or pericardial fluid requiring drainage.
- 11. Evidence of any active, uncontrolled bacterial, viral, parasitic, or systemic fungal infections within 1 week of the first dose of study drug.
- 12. Known active CNS metastases and/or carcinomatous meningitis or symptomatic brain metastasis. Participants with previously treated brain metastases may participate provided they are radiologically stable, i.e., without any of the following:
 - a. Evidence of progression for at least 4 weeks by repeat imaging,
 - b. Steroid treatment or stereotactic radiosurgery for at least 14 days prior to Cycle 1 Day 1,
 - c. Whole brain radiation therapy for at least 28 days prior to Cycle 1 Day 1.
- 13. Known or active other malignancies that have needed treatment (excluding palliative radiation) within 2 years prior to Cycle 1 Day 1 are excluded except for the following:
 - a. Curatively resected non-melanomatous skin cancer
 - b. Curatively treated cervical carcinoma in situ

- c. Non-metastatic breast and prostate cancer patients with stable disease > 12 months
- d. Other stable malignancies may be permitted based on Medical Monitor approval
- 14. Elective or a planned major surgery to be performed during the study.
- 15. History of allergic reactions attributed to Dox or other anthracyclines.
- 16. History of allergic reactions attributed to NaHA, hyaluronic acid, or gram-positive bacterial proteins.
- 17. Patients who have received a live vaccine within 28 days of Cycle 1 Day 1. See section [5.9.2 Prohibited Concomitant Treatment](#) for examples. Note: Seasonal influenza vaccines for injection are generally inactivated flu vaccines and are allowed; however, intranasal influenza vaccines (e.g., Flu-Mist®) are live attenuated vaccines and are not allowed.
- 18. History or evidence of a clinically unstable/uncontrolled disorder, condition, or disease (including but not limited to cardiopulmonary, renal, metabolic, hematologic, or neurologic) other than their primary malignancy, that in the opinion of the Investigator would pose a risk to patient safety or interfere with the study evaluation, procedures, or completion.

4.2. SPECIFIC INCLUSION/EXCLUSION CRITERIA FOR PHASE 2A EXPANSION GROUPS

4.2.1. Expansion Group 1: Extremity STS

4.2.1.1. Inclusion Criteria

- 1. Patients with unresectable soft tissue sarcomas of the extremity AJCC III OR select IV (>5 cm injectable tumors) locally advanced and or metastatic, not amendable to primary surgical intervention according to the consensus of a multidisciplinary treatment team, determined prior to screening.
 - Resectable is defined for the study as a primary surgical intervention that is thought to produce a surgical cure and maintain a good functional outcome of the affected extremity.
 - The assessment of resectability will be conducted by the multidisciplinary treatment team and study investigator and is typically defined by staging exams (CT scan of the chest, CT or MRI of the abdomen, MRI of the limb for extremity STS) and consultations with surgical oncology, radiology, and additional medical and surgical specialties as need.
- 2. High grade STS, Grade 2/3, with an assessable/injectable lesion of at least diameter >5 cm by RECIST 1.1 criteria
- 3. No prior chemotherapy for STS, or radiation to affected limb
- 4. Local disease candidates must meet one of the following criteria:
 - a. Candidates for radical excision or removal of anatomic compartment
 - b. Candidate for amputation where the gross total resection is considered to result in a non-functional limb

- c. Patients who refuse initial radical excision or amputation and who would prefer a neoadjuvant treatment approach
- d. Patients who are candidates for limb salvage radiation but decline radiation therapy
- 5. Patients who are candidates for neoadjuvant chemotherapy based on the location of the tumor and have clinical contraindications to standard of care or refuse neoadjuvant chemotherapy
- 6. Patients who have a recommendation from the multidisciplinary tumor board for single agent anthracycline
- 7. Only soft-tissue sarcomas of the following histologies are to be enrolled: leiomyosarcoma, liposarcoma, synovial sarcoma, adult fibrosarcoma, and undifferentiated pleomorphic sarcoma, angiosarcoma
- 8. Surgery can be deferred up to 12 weeks, in a clinically monitored patient on study

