This study will enroll male or female patients ≥ 18 years of age with an Eastern Cooperative Oncology Group (ECOG) performance status score of 0 or 1 and adequate organ function.

- A key exclusion criteria is prior lifetime exposure to >300 mg/m² of Dox HCl or DOXIL / CAELYX® or 600 mg/m² of epirubicin HCl or 600 mg/m² daunorubicin prior to study dosing.
- All patients must have a histologically or cytologically confirmed cancer or desmoid tumor.
- All patients must be either refractory to or relapsed following standard of care or ineligible for standard of care therapy

Phase 2: Dose Expansion will treat anthracycline naïve patients

- Group 1: patients with STS of the extremity who are ineligible for primary surgical resection and under consideration for possible/probable amputation with predefined anthracycline sensitive tumors histologies.
- Group 2: unresectable, locally advanced or metastatic STS with predefined anthracycline sensitive histologies
- Group 3:
 - 3a: relapsed or metastatic squamous-cell head and neck cancer (R/M HNSCC)

Phase 1 & 2a Tumor Requirements

The injected local or metastatic solid tumor must meet all the following criteria:

- A tumor type that is defined in where clinical evidence suggests that anthracyclines have favorable clinical activity. An injectable tumor defined as:
 - measurable per RECIST v1.1 at Baseline
 - palpable or able to be injected percutaneously with imaging guidance (i.e., ultrasound)
 - excluding the following organs/structures: pancreas and extrahepatic biliary tract, central nervous system, or heart and great vessels
 - accessible by repeated intra and/or peritumoral injection with a 18- to 22-gauge needle
- Phase 1 additional criteria for the 20 mL SQL70 biopolymer (from Cycle 1) Cohort:
 - Have at least two injectable tumors or, based on investigator clinical judgement documented in the medical record, a sufficiently large single lesion that can be injected with a 20 mL volume (i.e., 5 cm or larger).
- Anthracycline sensitive tumors for Phase 2a Groups 1 & 2 include:
 - Angiosarcomas
 - Leiomyosarcoma
 - Liposarcoma
 - Synovial sarcoma
 - Adult fibrosarcoma
 - Undifferentiated pleomorphic sarcoma

TREATMENT GROUPS AND REGIMENS

Phase 1: Dose Escalation

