2.2. PHASE 2A EXPANSION GROUPS

2.2.1. Objectives

2.2.1.1. Primary Objectives

- Further investigate the safety and tolerability profile of SQ3370 in anthracycline naïve patients with:
 - Group 1: Neo-adjuvant treatment of patients with STS of the extremity who are ineligible for primary surgical resection and under consideration for possible/probable amputation, with predefined anthracycline sensitive tumors.
 - Group 2: Patients with unresectable, locally advanced or metastatic STS, with predefined anthracycline sensitive tumors and compare safety and tolerability of the RP2D in two infusion schedules of SQP33 (3-day vs 5-day).
 - Group 3:
 - 3a) Patients with relapsed or metastatic squamous-cell head and neck cancer

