4.2.2.2. Exclusion Criteria

- 1. Prior exposure to anthracyclines
- 2. Treatment naïve extremity tumors (as they would enroll in Group 1)

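### Group 1 is described as anthracycline naïve, but its eligibility criteria do not enforce it, and the Phase 2a baseline table does not list prior anthracycline exposure

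*Protocol*

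**What the plan says.** **The population as described.** The synopsis (Study Population) states: "Phase 2: Dose Expansion will treat anthracycline naïve patients". The primary objective in protocol 2.2.1.1 is: "Further investigate the safety and tolerability profile of SQ3370 in anthracycline naïve patients with", followed by the list of groups, with Group 1 first. Section 3.3 defines Group 1 as "Anthracycline naïve patients with soft tissue sarcomas of the extremity AJCC Stage III OR select IV". The Phase 2a SAP, section 3.1, repeats the objective for Group 1 in the same terms.

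**The criteria that govern entry.** Protocol section 4 opens: "All patients in all Phase 1 cohorts and Phase 2a expansion groups must meet the inclusion and exclusion criteria below". Those that bear on prior anthracyclines are:

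- General exclusion 1 (4.1.2), for all cohorts and groups: "Prior lifetime exposure to >300 mg/m² of Dox HCl or DOXIL / CAELYX". The same item names 600 mg/m² for epirubicin and for daunorubicin.
- Group 1 inclusion 3 (4.2.1.1): "No prior chemotherapy for STS, or radiation to affected limb".
- Group 1 exclusions (4.2.1.2): three items, on pain, open wounds or necrosis, and compartment syndrome.
- Group 2 exclusion 1 (4.2.2.2): "Prior exposure to anthracyclines".
- Group 3a exclusion 2 (4.2.3.2): also an explicit bar on prior anthracycline treatment.

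**Baseline reporting.** Section 10.5 of the Phase 1 SAP lists prior anthracycline therapy and prior cumulative doxorubicin. Section 10.5 of the Phase 2a SAP lists neither, and its prior-therapy item covers only the cancer under study.

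**The concern.** The descriptive text and the operative criteria define different Group 1 populations. Two of the three expansion groups carry the bar and Group 1 does not, so the gap is specific to this group.

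What is at stake is the interpretation of the primary endpoint. Safety is the Phase 2a primary endpoint. Group 1 receives 20 mL of SQL70 and for that reason has its own run-in of six patients (protocol 3.2.7, Table 4). A patient who already carries anthracycline exposure is outside the population named in the objective, and any cardiac finding in that patient would be harder to attribute. If exposure is not tabulated, a reader of the summary tables could not tell how many such patients were included.

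**Working it through.** The check is mainly a comparison of texts.

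**1. Does any criterion applying to Group 1 require no prior anthracycline?**

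| Criterion | What it bars | Closes the gap? |
|---|---|---|
| 4.1.2 item 1 | Doxorubicin above 300 mg/m² | No; exposure up to and including 300 mg/m² passes |
| 4.1.2 item 3 | Anticancer therapy within 28 days, or 6 half-lives for small molecules | No; washout only |
| 4.1.2 item 13 | Other malignancy needing treatment within 2 years, with exceptions | No; narrows the route |
| 4.2.1.1 item 3 | Chemotherapy given for STS | No; silent on chemotherapy for another cancer |
| 4.2.1.1 item 6 | Nothing; concerns a tumor-board recommendation for a single-agent anthracycline | No |
| 4.2.1.2 items 1 to 3 | Local tumor complications | No |

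**2. Is there a route that the documents themselves allow?** Section 1.1 names breast cancer among the diseases treated with doxorubicin. General exclusion 13 exempts non-metastatic breast cancer stable for more than 12 months, and other stable malignancies with Medical Monitor approval. It does not reach cancers last treated more than 2 years ago. Take a patient with such a history, at most 300 mg/m² of prior doxorubicin, and a new, untreated extremity sarcoma. Group 2 excludes this patient twice: for the anthracycline, and because treatment-naïve extremity tumors are directed to Group 1. Group 1 has no matching bar.

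**3. Would the patient be caught afterwards?** Protocol 6.3 enrolls patients who meet all inclusion and exclusion criteria, with sponsor approval. Section 10.5.1 counts major violations of those criteria as important deviations. This patient violates none of them, so that item would not flag the case.

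**4. Would the exposure be reported?** Protocol 6.4 collects all prior cancer therapies, and section 9 of the Phase 2a SAP puts all database data in listings. It would therefore appear in listings, but no row for it is named in the baseline table.

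**5. Size.** One patient is 1/6 = 16.7% of the run-in and 1/46 = 2.2% of the full group.

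**6. Side check on the Group 1 design.** Exact binomial calculation of the two-stage rule (stop at 3 or fewer of 15; reject at 13 or fewer of 46) gives:

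- at a 20% response rate: alpha 0.0498, probability of early termination 0.648, expected sample size 15 + (1 − 0.648) × 31 = 25.91;
- at 35%: power 70.5%.

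All match protocol 8.3. The point made here does not alter these figures.

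**The case against.** The strongest reply is that the intent is plain. The synopsis and section 3.3 both state naïvety for Group 1, every enrollment needs documented sponsor approval (6.3), and the history must identify all prior cancer therapies (6.4). A pre-exposed patient would have to pass all of that. The route also needs an earlier anthracycline-treated cancer that escapes exclusion 13, followed by a rare new tumor. This stands as an argument about frequency. It does not remove the mismatch: a sponsor reviewer would have no written eligibility criterion on which to refuse.

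On reporting, the Phase 2a baseline list is expressly non-exhaustive. It shows an empty bullet where the Phase 1 list has prior anthracycline therapy, and the SAP carries a version 0.1 footer. The row may have been lost in drafting. Not tabulated is therefore the accurate description; not visible would be too strong.

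A reader might infer three further consequences that the documents do not support:

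- **Resistant disease.** Inclusion 3 means the sarcoma itself has had no chemotherapy directed at it. Nothing in the documents says that an anthracycline given for another cancer lowers its response.
- **A broken 20% null.** The text that ties historical rates to no prior anthracycline is written for Group 2 (protocol 8.3). Inclusion 3 keeps Group 1 chemotherapy-naïve for its sarcoma. Even if one or two of 46 patients had an assumed 20% response rate and the rest 35%, the average rates would be (45 × 0.35 + 0.20)/46 = 0.347 and (44 × 0.35 + 2 × 0.20)/46 = 0.343. Power would be 69.1% and 67.6%, against 70.5%.
- **A breached lifetime limit.** Setting 300 mg/m² against the 450–550 mg/m² in protocol 6.16.1 tells us nothing here. That limit is for doxorubicin. Section 10.8 of the Phase 2a SAP gives 250 mg/m² SQP33 at 12x; read as a daily dose, one cycle is 250 × 5 × 0.7153 = 894 mg/m² doxorubicin equivalent, nominally above the limit for every patient. The protocol also has an LVEF exclusion, repeated ECHO/MUGA and cardiac biomarkers.

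**Conclusion.** The inconsistency is real. Group 1 is named as anthracycline naïve in four places, and the criteria that decide entry admit a patient with prior anthracycline exposure for another cancer. Followed as written, they can place someone outside the primary-objective population in the safety analysis and the run-in.

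The effect is likely small: a few patients at most, with the run-in the place where a single one would weigh most. No expected number can be given, because the documents state no pre-exposed share. The conclusion rests on section 4 being the operative eligibility text, as its opening sentence and section 6.3 indicate. It does not extend to tumor resistance, the validity of the 20% null, or the lifetime doxorubicin limit. It is a low-priority correction, worth making because it is specific and nearly free.

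**What to change.** 1. **Protocol 4.2.1.** Reconcile the Group 1 criteria with 2.2.1.1, 3.3 and the synopsis. Reusing in 4.2.1.2 the prior-anthracycline exclusion that Groups 2 and 3a already carry would match the stated objective. If the sponsor does intend to admit limited prior exposure, the objective and the Group 1 description should say so instead.
2. **Phase 2a SAP 10.5.** Restore the two Phase 1 items, prior anthracycline therapy and prior cumulative doxorubicin, covering treatment for any cancer and not only the one under study.

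The cost is one protocol line and two rows in a baseline table, with no change to sample size or decision rules. Protocol 6.4 already collects prior cancer therapies; whether cumulative dose is recorded in the Phase 2a database should be confirmed. Any effect on accrual should be negligible, since few patients would be affected.
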